8.2 Randomization

All subjects who are screened (including screen failures) will be assigned a unique subject identification number.

On Day 1, eligible subjects will be assigned another unique number (randomization number) in sequential order. The randomization number codes the subject's initial treatment assignment according to the

randomization schedule generated prior to the study. Randomization will follow a permuted block design and will be stratified by use of HU (yes vs. no) and by region (North America/Europe vs. Africa/Middle East). Initially, subjects will be randomly assigned in a 2:1 ratio using a block size of 6 to receive either IMR-687 lower dose or placebo respectively. If the DMC recommends inclusion of the higher dose, randomization will then proceed in a 1:2:1 ratio (IMR-687 lower dose, IMR-687 higher dose, or placebo) using a block size of 4.

Randomization numbers will not be re-used once assigned. If a subject is replaced, the replacement subject will receive the same treatment assignment as the replaced subject, and a different leading number will be used for the replacement randomization number.

Randomization schedules were generated by Cytel, a subcontractor of the interactive voice/web response system (IXRS) vendor Suvoda.

9.0 Study Endpoints, Variables and Covariates

9.1 Primary Efficacy Endpoint

The primary endpoint is the annualized rate of VOCs

9.2 Safety Endpoints

Safety endpoints include the number and percentage of subjects with the following:

- At least one treatment-emergent adverse events (AEs)
- At least one treatment-emergent serious adverse events (SAEs)
- At least one clinically significant change in a laboratory test parameter
- At least one clinically significant change in a vital signs parameter
- At least one clinically significant change in an electrocardiogram (ECG) parameter

9.3 Secondary Efficacy Endpoints

- Key secondary efficacy endpoint 1: Time to first VOC
- Key secondary efficacy endpoint 2: Proportion of HbF responders (defined as proportion of subjects with an absolute increase of $\geq 3\%$ in HbF from baseline) at Week 24
- The study has the following additional secondary endpoints:
 - Proportion of VOC-free subjects
 - Annualized rate of VOC-related hospitalizations
 - Annualized rate of days hospitalized for VOC-related hospitalizations
 - Time to second VOC
 - Proportion of HbF responders (defined as proportion of subjects with an absolute increase of $\geq 3\%$ in HbF from baseline) at Week 52
 - Proportion of Hb responders (defined as proportion of subjects with an absolute increase of ≥ 1.0 g/dL in total Hb from baseline) at Week 24 and Week 52
 - Change from baseline in the following at Weeks 24 and 52:
 - HbF (%), F-cells (%), total Hb (g/dL)
 - Biomarkers of red blood cell (RBC) hemolysis (% and absolute reticulocytes, unconjugated [indirect] bilirubin, and lactate dehydrogenase (LDH))

- Each measured subdomain of the Adult Sickle Cell Quality of Life Measurement Information System (ASCQ-Me) questionnaire
- Total preference score and individual domain scores of the Patient-Reported Outcomes Measurements Information System – Preference (PROMIS 29 + 2 Profile v2.1 [PROPr]) questionnaire
- Overall score of the Sickle Cell Self-Efficacy Scale (SCSES)
- Change from baseline in biomarkers of adhesion including soluble E-selectin (E-sel), P-selectin (P-sel), intercellular adhesion molecule 1 (ICAM-1), and vascular cell adhesion molecule 1 (VCAM-1) at Week 24 and Week 52
- Biomarkers of inflammation such as high-sensitivity C reactive protein (hsCRP) and myeloperoxidase [MPO]
- Biomarkers of cardiac stress such as N-terminal prohormone of brain natriuretic peptide (NT-proBNP)
- RBC indices, such as mean corpuscular volume (MCV)

9.4 Secondary Pharmacokinetic Endpoint

PK will be assessed for IMR-687 (where feasible)

- PK profile (concentration-time measurements) and population PK of IMR-687

9.5 Exploratory Endpoints

- Renal Function
 - Change from baseline in renal function as measured by the urine protein-to-creatinine (Pr:Cr) ratio, microalbumin, and urine Cystatin Cat Week 24 and Week 52
- VOCs:
 - Number and percentage of subjects with at least 1 VOC event
 - Number and percentage of subjects by category of number of VOC events: 0, 1, 2-4, 5-7, 8-12, 13+
 - Number of and percentage of subjects with at least one VOC event lasting for ≥ 48 hours
 - Number and percentage of subjects with complicated VOCs (ACS, priapism, hepatic or splenic sequestration)
 - Number and percentage of subjects with at least 1 ACS
 - Number and percentage of males with priapism
 - Number and percentage of subjects with hepatic or splenic sequestration
 - Number of and percentage of subjects with uncomplicated VOCs
 - Time to first event of complicated VOCs
 - Annualized rate of days of VOCs (in days)
 - Annualized rate of VOCs, excluding subjects with a short period of exposure (e.g. <4 weeks)
 - Annualized rate of uncomplicated VOCs

- VOC-Related Hospitalizations:
 - Number and percentage of subjects with at least 1 VOC-related hospitalization
 - Number and percentage of subjects by category of number of VOC-related hospitalizations: 0, 1, 2-4, 5-7, 8-12, 13+
- RBC Transfusions:
 - Time to first RBC transfusion
 - Number and percentage of subjects with at least 1 RBC Transfusion
- Relationships between VOC and PD parameters
 - Correlation of annualized rate of VOCs and PD parameters (e.g., HbF, Hb and F-cells) with each other, at Week 24 and Week 52, for HU and non-HU use subgroups separately and together

10.0 Conventions and Derivations

10.1 Method for Handling Missing Data

There will be no imputation of incomplete or missing data unless specified otherwise in this SAP.

Please refer to [Appendix 4](#) for specific data handling rules, including missing last dose date for IA, incomplete/missing dates for adverse events and prior/concomitant medications, interpretation of non-numeric results (e.g. “< BLQ”, “>x.xx”) from PK and laboratory measures, etc.

Efficacy and PK imputation for missing data will be detailed in [Section 13.5](#).

Imputation will be noted in the footnotes. The original values/results will be presented in the data listings.

10.2 Definitions of Baseline and Change from Baseline Values

Unless otherwise specified, baseline is defined as the last non-missing measurement prior to the first dose of study drug.

All ECG assessments at a visit are to be performed in triplicate at each scheduled visit. The baseline value for ECG parameters will be derived as the average of all non-missing values, at the last visit prior to the first dose of study drug. Post-baseline assessments at a visit will be averaged for analysis.

In analyses of pharmacodynamics (PD) parameters, baseline is defined as the average of non-missing values from the screening and baseline visits. PD assessments include the following laboratory measurements based on blood samples (HbF-associated biomarkers and total Hb; biomarkers of RBC hemolysis, adhesion, inflammation, and cardiac stress; RBC indices).

Change from baseline at a post-baseline visit is defined as follows:

- For the ECG parameters: Post-Baseline Average Value – Baseline Average Value
- For PD parameters: Post-Baseline Value – Baseline Average Value
- For all other parameters: Post-Baseline Value – Baseline Value

10.3 Definitions of Study Days

Study Day 1 is defined as the date on which subjects are administered their first dose of study drug. For visits or events that occur on or after the first dose of study drug, study day is defined as (date of visit [event] – date of first dose of study drug + 1). For visits (or events) that occur prior to Study Day 1, study day is defined as (date of visit [event] – date of first dose of study drug). There is no Study Day 0.

10.4 Definition of Treatment-Emergent Adverse Event

A treatment-emergent adverse event (TEAE) is defined as an AE that emerges on or after initiation of study drug, or an AE that existed pre-treatment and worsened in severity on or after initiation of study drug, through 30 days after the last dose of study drug.

10.5 Windowing Conventions

All scheduled study visits are defined relative to Study Day 1, the date of first dose. Scheduled visit windows are defined in [Appendix 3](#). A windowing convention will be used to determine the analysis visit value for a given measurement and will be applicable for all by-visit summaries and analyses for efficacy and safety data. Refer to [Table 2](#) below for specific visit windows.

Table 2 Visit Windows for Efficacy and Safety Analyses

| For all Efficacy (Except for QoL) and PD Analyses | |
|---|--|
| Scheduled Study Visit (Protocol Scheduled Day) | Analysis Visit Window (Study Day) |
| Baseline | ≤ 1 |
| Week 4 (Day 28 ± 5) | 2 to 43 |
| Week 8 (Day 56 ± 5) | 44 to 71 |
| Week 12 (Day 84 ± 5) | 72 to 99 |
| Week 16 (Day 112 ± 7) | 100 to 141 |
| Week 24 (Day 168 ± 7) | 142 to 211 |
| Week 36 (Day 252 ± 7) | 212 to 309 |
| Week 52 (Day 364 ± 7) | ≥ 310 |
| For QoL Analysis | |
| Scheduled Study Visit (Protocol Scheduled Day) | Analysis Visit Window (Study Day) |
| Baseline | ≤ 1 |
| Week 4 (Day 28 ± 5) | 2 to 57 |
| Week 12 (Day 84 ± 5) | 58 to 127 |
| Week 24 (Day 168 ± 7) | 128 to 211 |
| Week 36 (Day 252 ± 7) | 212 to 309 |
| Week 52 (Day 364 ± 7) | ≥ 310 |
| For Safety Analysis | |
| Scheduled Study Visit (Protocol Scheduled Day) | Analysis Visit Window (Study Day) |
| Baseline | ≤ 1 |
| Week 1 (Day 7 ± 2) | 2 to 15 |
| Week 4 (Day 28 ± 5) | 16 to 43 |
| Week 8 (Day 56 ± 5) | 44 to 71 |
| Week 12 (Day 84 ± 5) | 72 to 99 |
| Week 16 (Day 112 ± 7) | 100 to 127 |
| Week 20 (Day 140 ± 7) | 128 to 155 |
| Week 24 (Day 168 ± 7) | 156 to 190 |
| Week 30 (Day 210 ± 7) | 191 to 232 |
| Week 36 (Day 252 ± 7) | 233 to 274 |
| Week 44 (Day 308 ± 7) | 275 to 337 |

| For Safety Analysis | |
|---|--|
| Scheduled Study Visit (Protocol Scheduled Day) | Analysis Visit Window (Study Day) |
| Week 52 (Day 364 ± 7) | 338 to 379 |
| Week 56 (Day 392 ± 7) | ≥ 380 |

Windowing will be applied prior to any missing data calculations. The last non-missing measurement taken prior to the date of first dose (including unscheduled assessments) will be labeled as “Baseline”. Unscheduled or Screening visits that occurred before the baseline visit will not be assigned an analysis visit. The early discontinuation visit will be eligible for allocation to an analysis visit.

If one or more results for a variable are assigned to the same analysis visit, the result with the date closest to the scheduled day per protocol will be used in the analysis. If 2 measurements in the same analysis visit window are equidistant from the scheduled study day, the earliest measurement will be used in the analysis. If multiple assessments are available on the same day (for the same time point), then the average of the assessment will be used in the analysis. If both central and local assessments of the same lab test are available on the same day, the central result will take precedence over the local result.

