Concomitant medications ⁱ																	Continuous	
Efficacy and Pharmacodynamic Assessments																		
Specialty hematology ^j	X	X			X		X	X	X		X		X		X		X	
PD biomarkers ^k	X	X			X		X	X	X		X		X		X		X	
QoL tools ^l		X			X			X			X		X		X		X	
CV marker	X	X						X			X		X		X		X	
Pharmacokinetic Assessments																		
IMR-687 plasma PK sampling ^m			X		X						X					X		
Study Drug Procedures																		
Study drug dispensing			X		X		X	X	X	X	X	X ⁿ	X ⁿ	X ⁿ	X ⁿ			
Study drug administration ^o																		
																	Oral administration IMR-687 or matching placebo qd	

Table 1 Schedule of Assessments (Continued)

Abbreviations: AE = adverse event; ASCQ-Me = Adult Sickle Cell Quality of Life Measurement Information System; BP = blood pressure; CV = cardiovascular; ECG = electrocardiogram; EOS = end of study; EOT = end of treatment; ET = early termination; F-cells = cells positive for HbF; HbF = fetal hemoglobin; HBsAg = hepatitis B surface antigen; HCV = hepatitis C virus; HR = heart rate; HU = hydroxyurea; ICAM-1 = intercellular adhesion molecule 1; IgM = immunoglobulin M; MPO = myeloperoxidase; NA = not applicable; PD = pharmacodynamic; PE = physical examination; PK = pharmacokinetics; Pr:Cr = protein-to-creatinine (ratio); PROPr = Patient-Reported Outcomes Measurements Information System – Preference; qd = once daily; QoL = quality of life; SCSES = Sickle Cell Self-Efficacy Scale; TEAE = treatment-emergent adverse event; VCAM-1 = vascular cell adhesion molecule 1.

Note: Unscheduled visits may occur, limited to visits resulting from potential TEAEs, drug dispensation, or other urgent study-related procedures.

^a Day 1 assessments should be performed prior to study drug administration.

^b All inclusion and exclusion criteria will be assessed at the Screening Visit; continued eligibility based on these criteria will be confirmed on Day 1.

^c Qualified site personnel will contact the subject at Week 2 and Week 6 to capture potential TEAEs and concomitant medications. Subjects will also be reminded of compliance with drug and the next visit schedule. If any AEs of significant clinical concern are identified during the telephonic visit, the subject will be requested to come into the site to be assessed.

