13.5.8 Safety Analyses

In general, safety analyses will be based on the safety analysis set and will be provided by treatment group as defined in [Section 11.1](#). The "Total" column will not be included in the summary tabulations.

Visit windowing (as specified in [Section 10.5](#)) will be used to determine the analysis visit for laboratory, vital sign and ECG by-visit analyses.

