Shift tables representing the shift from the baseline grade to maximum NCI-CTCAE Grades (Grade I to IV and Missing) will be provided for selected hematology and chemistry parameters by visit by treatment group. See [Appendix 5](#) for details.

Potentially clinically significant (PCS) Criteria for hepatic function and renal function are shown in [Table 9](#) below. The number and percentage of subjects meeting these PCS criteria will be summarized for hepatic function parameters (ALT, AST, ALP, and total bilirubin) and the renal function parameter (serum creatinine) separately. Any subject with any post-baseline result (including “unscheduled” visits) meeting the criteria will be included in the tabulation.

Table 9 PCS Criteria for Hepatic Function and Renal Function

| Hepatic Function | Renal Function |
|--|---|
| 
 ○ Post-baseline Alanine Aminotransferase (ALT) $\geq 3 \times$ upper limit of normal (ULN) ○ Post-baseline Aspartate Aminotransferase (AST) $\geq 3 \times$ ULN ○ Post-baseline Direct Bilirubin (BILDIR) $\geq 2 \times$ ULN ○ Post-baseline ALT/AST and BILDIR (ALT $\geq 3 \times$ ULN or AST $\geq 3 \times$ ULN) and BILDIR $\geq 2 \times$ ULN (Hy's Law) | 
 ○ Post-baseline Creatinine Clearance (CREATCLR) $< 0.5 \times$ baseline ○ Post-baseline Serum Creatinine (CREAT) $> 2 \times$ baseline |

Creatinine clearance are not directly collected and will be calculated using the Crockroft Gault formula:

$$CrCl = \frac{(140 - \text{patient's age in years}) \times \text{Body weight in kg}}{72 \times \text{serum creatinine in mg/dl}}$$

All laboratory parameters (serum chemistry, central laboratory hematology, local laboratory hematology, specialty hematology, coagulation, and urinalysis) will be displayed in individual subject data listings.

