| 8. Multiple assessments for the same visit | Vital Sign, ECG and Laboratory assessments | 
 All ECG assessments are to be performed in triplicate. Valid assessments will be averaged to get the analysis value for that visit. |

| Category | Description | Data Handling Rule |
|---|--|---|
| | | 
 • Other than for ECG assessments, the last non-missing measurement taken prior to the date/time of first study drug (including unscheduled assessments) will be the analysis baseline. • Windowing will be applied for by-visit analyses. Unscheduled or Screening visits that occurred before the Baseline visit will not be assigned an analysis visit. The early discontinuation visit will be eligible for allocation to an analysis visit. • If one or more results for a variable are assigned to the same analysis visit, the result with the date closest to the protocol scheduled day will be used in the analysis. If 2 measurements in the same analysis visit window are equidistant from the protocol scheduled study day, the earliest measurement will be used in the analysis. • If multiple assessments are available on the same day (or for the same time point for ECG assessments), then the average of the assessments will be used in the analysis. • If both central and local assessments of the same lab test are available on the same day, the central result will take precedence over the local result. • All data will be listed in data listings. |
| 9. Special Lab Value Handling | Lab values with a prefix such as: '>', '<', '+' and 'Less than' Etc. | 
 • '>': use the available original value +0.001 in the analyses. • '<': use the available original value -0.001 in the analyses. • '+': use the available original value without the prefix in the analyses. • '≥': use the available original value in the analyses. • '≤': use the available original value in the analyses. |

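### Keeping only the laboratory value nearest the target day conflicts with a by-visit shift to maximum CTCAE grade, so worse unscheduled values can drop out of the shift tables

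*SAP*

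**What the plan says.** SAP 10.5 sets up analysis windows that "will be applicable for all by-visit summaries and analyses for efficacy and safety data". Where more than one result falls in a window, "the result with the date closest to the scheduled day per protocol will be used in the analysis". Ties go to the earlier result: "If 2 measurements in the same analysis visit window are equidistant from the scheduled study day, the earliest measurement will be used in the analysis". Results from the same day are averaged, and a central result takes precedence over a local one. The only unscheduled visits kept out of the windows are early ones: "Unscheduled or Screening visits that occurred before the baseline visit will not be assigned an analysis visit". Later unscheduled results therefore enter a window and compete with the scheduled result.

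Appendix 4 item 8, the row for vital signs, ECG and laboratory assessments, repeats the rule: "the result with the date closest to the protocol scheduled day will be used in the analysis". Section 13.5.8 says that windowing "will be used to determine the analysis visit for laboratory, vital sign and ECG by-visit analyses".

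Section 13.5.8.2 plans "Shift tables representing the shift from the baseline grade to maximum NCI-CTCAE Grades", by visit and treatment group, for the haematology and chemistry parameters graded in Appendix 5. It does not say which results the maximum is taken over. In contrast, the hepatic and renal criteria (13.5.8.2), the vital-sign criteria (13.5.8.3) and the QTcF criteria (13.5.8.4) each state that unscheduled results count.

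The note to Protocol Table 1 reads: "Unscheduled visits may occur, limited to visits resulting from potential TEAEs". It goes on to name drug dispensing and other urgent study procedures as further reasons.

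**The concern.** A nearest-day rule suits means and changes from baseline, where each subject should contribute one comparable value per visit. A table of worst grades has the opposite aim. If the single selected value feeds the shift table, the grade shown is the grade near the target day, not the maximum.

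The loss would be selective. Some unscheduled visits take place because a subject may be having an adverse event, and blood drawn then is more likely to be abnormal than a routine draw. A short-lived Grade 3 or 4 cytopenia or electrolyte change found in this way could be missing from the one planned table that grades these parameters by arm.

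Haematology matters particularly here. Protocol 5.2 anticipates that IMR-687 will avoid the myelosuppression seen with hydroxyurea and will not need the same frequent blood-count monitoring. Graded counts bear directly on that expectation.

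**Working it through.** The plan gives no figure to reproduce. The check has two parts: what the text implies, and how often the literal rule would discard an unscheduled value.

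**Text.** Section 10.5 covers all by-visit safety analyses, Appendix 4 item 8 names laboratory assessments, and the shift tables are by visit. No sentence exempts them. Yet 13.5.8.2 asks for a maximum. Three readings are open: the maximum over all results in the window, the maximum over all post-baseline results, or the grade of the one selected value. The SAP does not choose, so two programmers could each follow it and produce different tables.

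**Days on which an unscheduled result must lose.** Protocol Table 1 visit tolerances, Week 1 to Week 52, cover 5 (Day 7 ± 2) + 3 × 11 (Days 28, 56, 84 ± 5) + 7 × 15 (Days 112, 140, 168, 210, 252, 308, 364 ± 7) = 143 days. Day 2 to Day 371 is 370 days, so 370 − 143 = 227 days (61%) lie outside every tolerance. A result on any of these days is farther from its target than any on-time scheduled draw in the same window, and loses to it.

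**Enumeration over the SAP Table 2 safety windows.** Our assumptions, which are not in the documents: one scheduled and one unscheduled result per window, and the unscheduled day uniform over the window. Let n be the window length, w the tolerance, and d the offset of the scheduled draw from its target day. Under the nearest-day, earliest-if-tied and same-day-average rules, the number of unscheduled days discarded is:

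- d = 0: n − 1
- scheduled draw early by k days: n − 2k
- scheduled draw late by k days: n − 2k − 1
- averaged over d uniform on −w to +w: n − (w + 1)

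| Visit | w | n | Discarded, draw on target | Discarded, draw uniform over tolerance |
|---|---|---|---|---|
| Week 1 | 2 | 14 | 13 (92.9%) | 11 (78.6%) |
| Weeks 4, 8, 12 (each) | 5 | 28 | 27 (96.4%) | 22 (78.6%) |
| Weeks 16, 20 (each) | 7 | 28 | 27 (96.4%) | 20 (71.4%) |
| Week 24 | 7 | 35 | 34 (97.1%) | 27 (77.1%) |
| Weeks 30, 36, 52 (each) | 7 | 42 | 41 (97.6%) | 34 (81.0%) |
| Week 44 | 7 | 63 | 62 (98.4%) | 55 (87.3%) |
| All windows | | 378 | 367 (97.1%) | 301 (79.6%) |

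With the scheduled draw at the edge of its tolerance, the share falls to between 13/28 = 46% (Weeks 16 and 20, draw 7 days late) and 49/63 = 78% (Week 44, draw 7 days early). On the remaining days the unscheduled result is selected or, if drawn the same day, averaged. If the scheduled result is missing, the unscheduled one is used.

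**Example.** The Week 44 window runs from Day 275 to Day 337 (63 days). A Grade 4 neutrophil count on Day 290 is 308 − 290 = 18 days from target. An on-time Week 44 draw is at most 7 days away. If the count is normal again at that draw, the literal table shows no abnormality at Week 44.

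**The case against.** The best reply is that the word maximum is specific to this table and makes no sense with one value per visit, so a sensible programmer would grade every result assigned to the window. Section 13.5.8 supports this a little: it says only that windowing determines the analysis visit, and does not restate the nearest-day choice. This stands as a possible reading. It does not settle the matter, because 10.5 and Appendix 4 item 8 state the selection rule without exception.

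The second reply is that other outputs show the worst values. The hepatic and renal criteria use any post-baseline result. Clinically significant laboratory results are recorded as AEs (Protocol 11.3.6), and AEs are graded and tabulated by severity without visit windows (SAP 13.5.8.1). SAP 9.2 lists subjects with at least one clinically significant laboratory change as an endpoint, and every value is listed. This cover is real but partial. The hepatic and renal criteria do not reach haematology or electrolytes. An abnormal value becomes an AE only if the investigator judges it clinically significant (Protocol 12.1.2.2.1). The 9.2 endpoint has no stated method beyond the hepatic and renal criteria. Listings give no comparison between arms.

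Third, the day counts do not measure bias. Unscheduled visits are not all prompted by adverse events, and the protocol note concerns visits rather than blood draws. Protocol 4.2.3.1 reports no significant change in white cells, platelets or neutrophils in healthy volunteers. All of this stands, and it limits what can be said about size.

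**Conclusion.** The nearest-day rule and the maximum-grade shift tables conflict. Under the literal rule, worse unscheduled values can drop out of those tables. Graded laboratory toxicity outside the hepatic and renal set may be understated as a result.

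A reader might infer more: that worst values will be lost and that laboratory toxicity is understated. The documents do not support that. The wording allows a reading that keeps these values. An unscheduled result is used when the scheduled one is missing or farther from target, and is averaged if drawn on the same day. Hepatic and renal extremes are counted elsewhere.

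The shares of 80% (scheduled draw uniform over its tolerance) and 97% (draw on target) describe days on which a value would be discarded, under one scheduled and one unscheduled result per window and uniform timing. They are not estimates of missed toxicity. That cannot be computed: the documents give no rate of unscheduled draws, no grade distribution and no difference between arms.

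**What to change.** 1. In SAP 10.5 and Appendix 4 item 8, limit nearest-day selection for safety laboratory data to by-visit descriptive statistics and changes from baseline.
2. In 13.5.8.2, state that the shift tables use the worst grade among all valid post-baseline results in each safety window, unscheduled results included. Do this separately for each direction where Appendix 5 grades both (for example haemoglobin, potassium and sodium).
3. Preferably add one row for the overall worst post-baseline grade. This is an extra output rather than a correction, but it removes any dependence on windows.
4. State how local-laboratory results without a same-source baseline are handled. Section 13.5.8.2 compares post-baseline values only with a baseline from the same source, so a local draw during an illness could otherwise stay outside the table even after changes 1 and 2.

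The cost is SAP wording in three places and a small programming change, with no effect on trial conduct. Reported grades may become slightly less favourable in every arm.
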